16.3.3. Other considerations[46]

1. Volumetric criteria are currently experimental and the existing data is not strong enough to support the universal requirement of volumetric response criteria in clinical trials. Nevertheless, the RANO-BM working group believes that assessment and reporting of

volumetric data and response will further research in this future and encourage its inclusion as a secondary endpoint when feasible. For investigators choosing to report volumetric response data, please note the following recommendations.

- a. Partial volumetric response should be defined as 65% or greater decrease in the sum volume of CNS target lesions, in addition to the corticosteroid and clinical status criteria outlined previously.
- b. Volumetric response should be reported as a waterfall plot to provide a global sense of potential efficacy.
2. Response of non-CNS (extracranial) disease should be assessed separately from CNS (intracranial) disease. Typically RANO-BM would be used for CNS disease and RECIST 1.1 for non-CNS disease. As this trial does not involve the assessment of non-CNS disease, RECIST 1.1 is excluded from this protocol.
3. Please refer to Table 16-5 for RANO-BM recommendations for bi-compartmental assessment of response, i.e. when considering local control and distant brain failure separately.

Table 16-4. Summary of the response criteria for CNS metastases proposed by RANO-BM[46]

	Complete response	Partial response	Stable disease	Progressive disease
Target lesions	None	≥ 30% decrease in sum longest distance relative to baseline	< 30% decrease relative to baseline but < 20% increase in sum longest distance relative to baseline	≥ 20% increase in sum longest distance relative to nadir*
Non-target lesions	None	Stable or improved	Stable or improved	Unequivocal progressive disease
New lesion(s)^\wedge	None	None	None	Present*
Corticosteroids	None	Stable or decreased	Stable or decreased	Not applicable#
Clinical status	Stable or improved	Stable or improved	Stable or improved	Worse*
Requirement for response	All	All	All	Any#

*Progression occurs when this criterion is met.

^\wedge A new lesion is one that is not present on prior scans and is visible in a minimum of two projections. If a new lesion is equivocal, for example because of its small size, continued therapy can be considered, and follow-up assessment will clarify if the new lesion is new disease. If repeat scans confirm there is definitely a new lesion, progression should be declared using the date of the initial scan showing the new lesion. For immunotherapy-based approaches, new lesions alone do not define progression.

#Increase in corticosteroids alone will not be taken into account in determining progression in the absence of persistent clinical deterioration.

Table 16-5. Sites of inclusion for assessment of bi-compartmental CNS outcomes.[46]

	Local CNS lesions	Distant CNS lesions	Non-CNS lesions*
Bi-compartmental progression-free survival*	x	x	x
CNS progression-free survival	x	x	
Non-CNS progression-free survival*			x
CNS_{local} progression-free survival	x		

*Non-CNS disease is not assessed in the current protocol.

16.4. Appendix 4. Hopkins Verbal Learning Test - Revised (HVLT-R)

Patient ID _____

Date of Evaluation _____

Patient Initials _____

Name of person administering tests _____

HOPKINS VERBAL LEARNING TEST (HVLT) - FORM 1

Instructions: Read the list of 12 words in Part A (at a rate of 1 word every 2 seconds), then have the patient repeat as many of the words as s/he can recall. Do this for 3 trials. After completing Trial 3, continue to Part B. Read each word and ask the patient to respond with "Yes" if the word was on the list or "No" if it was not.

After ALL Neurocognitive tests have been administered to the patient for this visit, ask the patient to recall the words you read to them at the beginning of the test. Mark the box next to each word the patient accurately recalls for each trial.

FREE RECALL & RECOGNITION: Semantic Categories: Four-Legged Animals, Precious Stones, Human Dwellings

1. PART A - FREE RECALL: For each trial, mark the box next to each word the patient accurately recalls for each trial.

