7.2. Neurocognitive Function Assessment

Neurocognitive function assessment will be performed using the HVLT-R Neurocognitive assessment will be performed on all patients during a clinic visit at baseline (i.e., before first treatment, at the time of simulation if possible) and 3, 6, and 12 months after treatment ends.

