7.2.1. HVLT-R

The HVLT-R is a 12 noun list with 4 words each from 1 or 3 semantic categories that are learned over the course of three learning trials. After 20-25 minutes, delayed recall and recognition are also assessed. This test is estimated to take 5-10 minutes with a 25 minute delay in the middle to allow for appropriate assessment of delayed recall. The focus of this test is on assessing verbal learning and memory. Please see Appendix 4 for a sample of one of the forms for the HVLT-R. The forms used for study will need to be purchased. This test may be administered remotely per the discretion of the PI.

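### Sections 1.4 and 7.2.1 and the Appendix 4 sample form disagree on when HVLT-R recognition and delayed recall are given, and the form sets no minimum delay

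*Combined protocol and SAP*

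**What the plan says.** Section 7.2.1 describes the test as three learning trials of a 12-word list and then states: "After 20-25 minutes, delayed recall and recognition are also assessed". It repeats the point when it estimates testing time, "with a 25 minute delay in the middle to allow for appropriate assessment of delayed recall". Section 1.4 carries the same description. In the body of the protocol, recognition and delayed recall therefore both follow the wait.

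The form in Appendix 4 (section 16.4) runs differently. After the three trials of Part A it says "After completing Trial 3, continue to Part B", and Part B is recognition. Delayed recall (Part C) has its own cue: "After ALL Neurocognitive tests have been administered to the patient for this visit, ask the patient to recall the words". The form's instructions mention no number of minutes.

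Section 7.2 names a single instrument: "Neurocognitive function assessment will be performed using the HVLT-R". Section 7.2.1 calls the Appendix 4 page a sample of one form and says that the forms for the study have to be purchased. Testing takes place at baseline and at 3, 6 and 12 months, and may be done remotely.

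Section 10.9 gives HVLT-R the only inferential test among the quality-of-life, neurocognitive and performance-status measures: a Wilcoxon rank sum comparison of change from baseline with the RTOG 0933 results.

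**The concern.** Delayed recall is meant to show what the patient retains after an interval. Two features of the form work against that. Its cue for delayed recall assumes a battery of tests that fills the time, and this trial has no such battery. It also has the examiner read every list word once more before recall is tested. Both would be expected to make recall easier.

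A further risk is inconsistency. With two texts in one protocol, one tester may wait 25 minutes and another may not, or the same patient may be tested differently at baseline and at 6 months. The secondary outcome in section 3.2 is change from baseline at 6 months, with 20 evaluable patients planned per cohort. Variation of this kind would enter the change scores directly, and it would be hard to find afterwards because the form as reproduced has a date field but no field for clock times.

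The measure matters to the trial's rationale. Section 1.6 suggests that a lower brain dose may improve neurocognitive function, HVLT-R is the only neurocognitive instrument, and the RTOG 0933 result cited in section 1.2 is for Delayed Recall.

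**Working it through.** There is no power or sample-size figure to reproduce. The check compares the two sets of instructions, counts words and bounds the interval.

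**Order and timing**

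| Step | Sections 1.4 and 7.2.1 | Appendix 4 form |
|---|---|---|
| Learning trials | 3 | 3 ("Do this for 3 trials") |
| Recognition | after 20-25 minutes | directly after Trial 3 |
| Delayed recall | after 20-25 minutes | when all neurocognitive tests of the visit are done |
| Minimum interval | 20-25 minutes (restated as 25) | none stated |

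The position of recognition conflicts on any reading. The timing of delayed recall does not strictly conflict, because a tester can satisfy both texts by waiting 20-25 minutes before Part C. The form does not tell the tester to wait.

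**What could fill the interval.** Sections 1.4, 2.2, 3.2, 7.2 and 10.9 name HVLT-R and no other neurocognitive test. The study calendar has one generic line for neurocognitive assessment. FACT-Br is a self-administered quality-of-life questionnaire that may be completed at home (section 7.3.1), so it neither counts as a neurocognitive test nor secures the time. The form's cue is thus met when Part B ends.

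**Bound on the interval.** Section 7.2.1 estimates 5-10 minutes for the test, with a 25 minute delay in the middle. Since 25 exceeds 10, the 5-10 minutes must be testing time without the delay. If only the form is followed and nothing else is inserted, the gap between Trial 3 and delayed recall is the time taken by Part B, which is part of those 5-10 minutes and so under 10 minutes. Against the 20 minute lower limit, the shortfall would be more than 20 - 10 = 10 minutes. After the last reading of the list words in Part B, the gap could be close to zero.

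**Exposure to the words.** Part B was compared with Part A word by word.

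- Part A: 12 list words.
- Part B: 24 words = 12 list words + 6 starred words + 6 other words. None of the 12 list words is missing.
- Readings of each list word before delayed recall on the form's order: 3 learning trials + 1 recognition reading = 4.
- Readings before the wait on the section 7.2.1 description: 3. The count at delayed recall stays at 3 only if recall is given before recognition. Section 7.2.1 lists them in that order but does not expressly require it.

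**The case against.** The strongest reply is that the Appendix 4 page may never be used. It is a sample, the study forms are to be purchased, and their instructions are not in the documents. Section 1.4 also requires trained and certified testers, and sections 1.4 and 7.2.1 both state the delay. This stands as a limit on how likely the problem is. It does not remove the problem, because nothing says which text governs if they differ, and the appendix is the only step-by-step script in the protocol.

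Four stronger readings are tempting, and the documents do not support them.

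- A reader might infer that delayed recall will be given with no delay. That requires a tester to follow the sample form alone and disregard the body text. Silence about the interval is not an instruction to skip it.
- A reader might infer that the form is the only administration instruction. Sections 1.4 and 7.2.1 also instruct on the delay.
- A reader might infer that the comparison with RTOG 0933 is invalid. The documents do not show the order in which that study gave recognition and delayed recall. If it used the order on the sample form, moving recognition could reduce comparability. Section 10.9 also does not name delayed recall as the score compared, and free recall over Trials 1-3 precedes Part B and is untouched.
- A reader might infer that decline will be masked. A feature common to every visit may partly cancel in change from baseline. That protection is partial and fails if visits are run differently.

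**Conclusion.** The inconsistency is real and worth correcting before testing continues. The protocol body and the sample form disagree on when recognition is given, and the form's cue for delayed recall secures no interval in a trial with one neurocognitive test. For a tester who follows the form alone, the delay falls from 20-25 minutes to under 10 minutes and possibly near zero after the last reading of the words, with four readings of each word instead of three.

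This rests on three assumptions: that the purchased forms resemble the sample, that nothing else fills the interval, and, for the count of three, that recall comes before recognition under section 7.2.1. The effect on scores and on the RTOG 0933 comparison cannot be determined from the documents. The point concerns part of one secondary measure and leaves the primary endpoint and sample size unaffected.

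**What to change.** Reconcile Appendix 4 with sections 1.4 and 7.2.1 so that one stated instruction governs.

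1. Fix the order of recognition and delayed recall explicitly, and state the 20-25 minute interval once, measured from a named point such as the end of Trial 3.
2. Replace the form's end-of-all-tests cue with that timed interval.
3. Check the purchased forms against the instruction and say that the protocol text prevails if they differ. Before settling the order, check which order RTOG 0933 used, since section 10.9 compares against it.
4. Apply the same instruction at baseline and at 3, 6 and 12 months, in person and remotely. Recording start and recall clock times would be a useful addition, because it makes adherence checkable.

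The cost is a short edit to the protocol text and form, and a note in tester training. Visit length does not change, because the 25 minute delay is already planned. If patients have already been tested, record which order and interval were used for them.

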3. PART C - DELAYED RECALL

	Trial 1	Trial 2	Trial 3	Delayed Recall
LION				
EMERALD				
HORSE				
TENT				
SAPPHIRE				
HOTEL				
CAVE				
OPAL				
TIGER				
PEARL				
COW				
HUT				

2. PART B - RECOGNITION: "x" Yes or No beside each word to indicate the patient's response.

Y	N	Y	N	Y	N	Y	N	Y	N	Y	N						
HORSE			ruby*			CAVE			balloon			coffee			LION		
house*			OPAL			TIGER			boat			scarf			PEARL		
HUT			EMERALD			SAPPHIRE			dog*			apartment*			penny		
TENT			mountain			cat*			HOTEL			COW			diamond*		

4. Discontinued: Testing discontinued? Yes (Complete the Neurocognitive Tests Discontinued/Not Done CRF)

No

RETAIN DATA SHEETS IN PATIENT STUDY FILE

16.5. Appendix 5. Functional Assessment of Cancer Therapy with Brain Subscale (FACT-Br)

Patient ID _____

FACT-Br (Version 4)

Patient Initials _____

Date of Evaluation _____

Below is a list of statements that other people with your illness have said are important. **Please circle or mark one number per line to indicate your response as it applies to the past 7 days.**

PHYSICAL WELL-BEING		Not at all	A little bit	Some- what	Quite a bit	Very much
GP1	I have a lack of energy	0	1	2	3	4
GP2	I have nausea	0	1	2	3	4
GP3	Because of my physical condition, I have trouble meeting the needs of my family	0	1	2	3	4
GP4	I have pain	0	1	2	3	4
GP5	I am bothered by side effects of treatment	0	1	2	3	4
GP6	I feel ill	0	1	2	3	4
GP7	I am forced to spend time in bed.....	0	1	2	3	4
SOCIAL/FAMILY WELL-BEING		Not at all	A little bit	Some- what	Quite a bit	Very much
GS1	I feel close to my friends.....	0	1	2	3	4
GS2	I get emotional support from my family	0	1	2	3	4
GS3	I get support from my friends.....	0	1	2	3	4
GS4	My family has accepted my illness	0	1	2	3	4
GS5	I am satisfied with family communication about my illness.....	0	1	2	3	4
GS6	I feel close to my partner (or the person who is my main support)	0	1	2	3	4
Q1	Regardless of your current level of sexual activity, please answer the following question. If you prefer not to answer it, please mark this box  and go to the next section.					
GS7	I am satisfied with my sex life	0	1	2	3	4

FACT-Br (Version 4)

Please circle or mark one number per line to indicate your response as it applies to the past 7 days.

EMOTIONAL WELL-BEING

		Not at all	A little bit	Some- what	Quite a bit	Very much
QE1	I feel sad	0	1	2	3	4
QE2	I am satisfied with how I am coping with my illness.....	0	1	2	3	4
QE3	I am losing hope in the fight against my illness.....	0	1	2	3	4
QE4	I feel nervous.....	0	1	2	3	4
QE5	I worry about dying.....	0	1	2	3	4
QE6	I worry that my condition will get worse.....	0	1	2	3	4

FUNCTIONAL WELL-BEING

		Not at all	A little bit	Some- what	Quite a bit	Very much
GF1	I am able to work (include work at home).....	0	1	2	3	4
GF2	My work (include work at home) is fulfilling.....	0	1	2	3	4
GF3	I am able to enjoy life.....	0	1	2	3	4
GF4	I have accepted my illness.....	0	1	2	3	4
GF5	I am sleeping well	0	1	2	3	4
GF6	I am enjoying the things I usually do for fun	0	1	2	3	4
GF7	I am content with the quality of my life right now.....	0	1	2	3	4

FACT-Br (Version 4)

Please circle or mark one number per line to indicate your response as it applies to the past 7 days.

ADDITIONAL CONCERNS		Not at all	A little bit	Some-what	Quite a bit	Very much
Br1	I am able to concentrate	0	1	2	3	4
Br2	I have had seizures (convulsions)	0	1	2	3	4
Br3	I can remember new things	0	1	2	3	4
Br4	I get frustrated that I cannot do things I used to.....	0	1	2	3	4
Br5	I am afraid of having a seizure (convulsion).....	0	1	2	3	4
Br6	I have trouble with my eyesight.....	0	1	2	3	4
Br7	I feel independent.....	0	1	2	3	4
NTX6	I have trouble hearing.....	0	1	2	3	4
Br8	I am able to find the right word(s) to say what I mean	0	1	2	3	4
Br9	I have difficulty expressing my thoughts	0	1	2	3	4
Br10	I am bothered by the change in my personality	0	1	2	3	4
Br11	I am able to make decisions and take responsibility.....	0	1	2	3	4
Br12	I am bothered by the drop in my contribution to the family	0	1	2	3	4
Br13	I am able to put my thoughts together.....	0	1	2	3	4
Br14	I need help in caring for myself (bathing, dressing, eating, etc.).....	0	1	2	3	4
Br15	I am able to put my thoughts into action.....	0	1	2	3	4
Br16	I am able to read like I used to	0	1	2	3	4
Br17	I am able to write like I used to.....	0	1	2	3	4
Br18	I am able to drive a vehicle (my car, truck, etc.).....	0	1	2	3	4
Br19	I have trouble feeling sensations in my arms, hands, or legs	0	1	2	3	4
Br20	I have weakness in my arms or legs.....	0	1	2	3	4
Br21	I have trouble with coordination	0	1	2	3	4
An10	I get headaches	0	1	2	3	4
